#### **2.5.5. Multiplicity Adjustment**

[figure not shown]
A sequential/hierarchical testing procedure will be used to control the overall Type 1 error rate at 0.05 (2-sided) over the primary endpoints, key secondary efficacy endpoints, and selected secondary endpoint. The hierarchical order for the hypotheses to be tested is indicated in [Figure 1](#).

The co-primary endpoints will be tested at the planned primary analysis at a 2-sided Type 1 error rate of 0.05. The success criteria of all 6 co-primary endpoints need to be met in order to declare the study a success to achieve noninferiority of coadministration.

The key secondary endpoints will only be tested at the primary analysis at a 2-sided Type 1 error rate of 0.05 when all co-primary endpoints have met success criteria of noninferiority. And the key secondary endpoints will be tested sequentially by GMR of RSV-B nAbs first, SRR of RSV-B nAbs second, then SCR of anti-HA Abs for each influenza strain last.

No further testing will be performed once the sequence/hierarch breaks, that is, further testing stops as soon as an endpoint in the sequence fails to meet success criterion of noninferiority. Analyses of remaining other secondary immune endpoints are not controlled for multiplicity.

**Figure 1** Testing Strategy of Co-primary and Key Secondary Immunogenicity Endpoints

## **2.5.6. Planned Analyses**

The following analyses will be conducted on cleaned data:

1. The primary analysis of safety and immunogenicity data will be performed after all participants have completed Day 29 visit.
2. The final analysis of all endpoints will be performed after all participants have completed Day 181/EoS. Results of this analysis will be presented in a final CSR. The final CSR will include full analyses of all safety and immunogenicity data through Day 181/EoS.

In addition, the DSMB will review unblinded primary analysis outputs to safeguard the interests of clinical study participants and to help ensure the integrity of the study. Unblinded data presentation or analysis for DSMB review will be handled by the unblinded statistics team from CRO, who are not involved in study design. More details regarding DSMB analysis can be found in the DSMB charter.

## **3. Part B**

### **3.1. Study Objectives**

#### **3.1.1. Primary Objectives**

##### **3.1.1.1. Primary Safety Objective**

The primary safety objective of the study is to evaluate the safety and tolerability of the mRNA-1345 vaccine coadministered with mRNA-1273.214.

##### **3.1.1.2. Primary Immunogenicity Objective**

The primary immunogenicity objectives are:

- 1) To evaluate the effect of coadministered mRNA-1273.214 on the immune response to RSV-A
- 2) To evaluate the effect of coadministered RSV vaccine on the immune response to SARS-CoV-2

#### **3.1.2. Secondary Objectives**

##### **3.1.2.1. Key Secondary Immunogenicity Objectives**

The key secondary immunogenicity objective is:

- To evaluate the effect of coadministered mRNA-1273.214 on the immune response to RSV-B

##### **3.1.2.2. Other Secondary Immunogenicity Objectives**

The other secondary immunogenicity objectives are:

- To evaluate the Ab response to mRNA-1345 with and without mRNA-1273.214
- To evaluate the Ab response to mRNA-1273.214 with and without mRNA-1345

### **3.1.3. Exploratory Objectives**

The exploratory objectives, which may be performed, is as follow:

- To further characterize the immune response across study vaccines

## **3.2. Study Endpoints**

### **3.2.1. Primary Endpoints**

#### **3.2.1.1. Primary Safety Endpoints**

The primary safety objective will be evaluated by the following safety endpoints:

- Numbers and percentages of participants with solicited local and systemic ARs over the 7 days after each injection.
- Numbers and percentages of participant with unsolicited AEs through 28 days after each injection.
- Numbers and percentages of participants with MAAEs, SAEs, AESIs, and AEs leading to withdrawal from Day 1 (baseline) to EoS.

#### **3.2.1.2. Primary Immunogenicity Endpoints**

The primary immunogenicity objectives will be evaluated by the following coprimary endpoints:

- GMT of serum RSV-A nAbs at Day 29.
- SRR in RSV-A nAbs at Day 29. Seroresponse for RSV-A nAbs is defined in the same way as for RSV-A nAbs in Part A, [Section 2.2.1.2](#).
- GMC of serum Ab level as measured by neutralization assay for SARS-CoV-2 at Day 29.
- SRR in SARS-CoV-2 nAbs at Day 29. Seroresponse for SARS-CoV-2 nAbs is defined in the same way as for RSV-A nAbs in Part A, [Section 2.2.1.2](#).

### **3.2.2. Secondary Endpoints**

#### **3.2.2.1. Key Secondary Immunogenicity Endpoints**

The key secondary immunogenicity objectives will be evaluated by the following endpoints:

- GMT of serum RSV-B nAbs at Day 29.

- SRR in RSV-B nAbs at Day 29. Seroresponse is defined in the same way as for RSV-A nAbs in Part A, [Section 2.2.1.2](#).

### 3.2.2.2. Other Secondary Immunogenicity Endpoints

The other secondary immunogenicity objectives will be evaluated by the following endpoints:

- GMT and GMFR of post-injection/baseline titers to RSV-A nAbs up to Day 211/EoS.
- GMT and GMFR of post-injection/baseline titers to RSV-B nAbs up to Day 211/EoS.
- SRR and proportion of participants with  $\geq 2$ -fold increases in RSV-A nAb titers up to Day 211/EoS. A  $\geq z$ -fold increase in RSV A nAb titers is defined in the same way as for RSV-A nAbs in Part A, [Section 2.2.2.2](#).
- SRR and proportion of participants with  $\geq 2$ -fold increases in RSV-B nAb titers up to Day 211/EoS. A  $\geq z$ -fold increase in RSV-B nAb titers is defined in the same way as for RSV-A nAbs in Part A, [Section 2.2.2.2](#).
- GMC and GMFR as measured by neutralization assay for SARS-CoV-2 up to Day 211/EoS.
- SRR and proportion of participants with  $\geq 2$ -fold increases in SARS-CoV-2 nAb up to Day 211/EoS. A  $\geq z$ -fold increase in SARS-CoV-2 nAb titers is defined in the same way as for RSV-A nAbs in Part A, [Section 2.2.2.2](#).

### 3.2.3. Exploratory Endpoints

- GMC and GMFR of post-injection/baseline concentration to RSV bAbs up to EoS.
- Proportions of participants with  $\geq 2$ -fold and  $\geq 4$ -fold increases in RSV bAb concentration up to Day 211/EoS. A  $\geq z$ -fold increase in RSV bAb concentration is defined in the same way as for RSV-A nAbs in Part A, [Section 2.2.2.2](#).
- GMC and GMFR of post-injection/baseline concentration to SARS-CoV-2 binding Abs up to Day211/EoS.
- Proportion of participants with  $\geq 2$ -fold and  $\geq 4$ -fold increases in SARS-CoV-2 binding Ab concentration up to Day 211/EoS. A  $\geq z$ -fold increase in SARS-CoV-2 bAb concentration is defined in the same way as for RSV-A nAbs in Part A, [Section 2.2.2.2](#).
- Frequency, specificities, or other endpoints to be determined for the further characterization of immune responses.

### 3.3. Study Design

#### 3.3.1. Overall Study Design

Part B is a Phase 3, randomized, observer-blind study to evaluate safety, tolerability, and immunogenicity of mRNA-1345, an mRNA vaccine targeting RSV, when given alone or coadministered with mRNA-1273.214 in adults  $\geq 50$  years of age.

All participants will participate in a Screening period (up to 14 days before Day 1), treatment period (vaccine and/or placebo administration on Day 1 [Baseline] and on Day 29), and a follow-up period (up to 7 months after first vaccination). The SoA is provided in [Appendix G](#).

The study will enroll approximately 1680 medically stable adults  $\geq 50$  years of age. On Day 1, each participant will receive 2 injections administered IM, one in each arm, in the deltoid muscle. Participants will be randomized as shown in Table 3 to receive either 1) mRNA-1345 (█ μg) + placebo (0.9% sodium chloride [normal saline]); 2) mRNA-1345 (█ μg) + mRNA-1273.214 (█ μg); or 3) mRNA-1273.214 (█ μg) + placebo. Randomization will be stratified by age (50 to 59 years, 60 to 74 years, and  $\geq 75$  years). The study will target enrollment of approximately 35% of participants 50 to 59 years of age. On Day 29, participants will receive an additional injection as outlined in Table 3 to allow all study participants to receive an mRNA-1273.214 booster vaccination.

**Table 3: Randomized Groups (Part B)**

Group Name	Sample Size	Vaccine Administered
Group 4	560	Day 1: mRNA-1345 (█ μg) + placebo in contralateral arms Day 29: mRNA-1273.214 (█ μg)
Group 5	560	Day 1: mRNA-1345 (█ μg) + mRNA-1273.214 (█ μg) in contralateral arms Day 29: placebo
Group 6	560	Day 1: mRNA-1273.214 (█ μg) + placebo in contralateral arms Day 29: placebo

Participants will have a total of 10 visits/safety telephone calls. At the dosing visits on Day 1 and Day 29, participants will be instructed how to document and report solicited ARs in a provided eDiary. Solicited ARs will be assessed from the day of injection and the following 6 days, and local solicited ARs will be assessed separately for each injection site. Unsolicited AEs will be

assessed from the days of injection and the following 27 days. SAEs, MAAEs, AEs leading to withdrawal, and AESIs will be assessed from Day 1 through EoS.

Blood sample collection for humoral immunogenicity will occur on Day 1, Day 29, Day 57, Day 181 and Day 211/EoS. The samples will be processed and analyzed as per the Laboratory Manual. The Day 8 visit (Visit 2) and Day 37 (Visit 4) may be either at the study site or a via a telephone call. The study site staff will perform scheduled safety telephone calls to participants on Day 91, Day 121, and Day 151 to collect AEs, MAAEs, AESIs, AEs leading to withdrawal, SAEs, and information about concomitant medications related to those events and receipt of non-study vaccinations.

### **3.3.2. Statistical Hypothesis**

The immunogenicity primary objectives are to evaluate the effect of coadministered mRNA-1273.214 on the immune response to RSV-A virus and SARS-CoV-2 (Wuhan-Hu-1 and B.1.1.529 strains). There are 6 co-primary endpoints to support the primary objectives.

#### **Primary Objective to Evaluate the Impact on the Immune Response to RSV-A:**

##### Co-primary endpoints based on GMT at Day 29:

The null hypothesis  $H_0^1$ : immunogenicity response to mRNA-1345 in participants who received mRNA-1345 coadministered with mRNA-1273.214 at Day 1, as measured by GMT at Day 29 using RSV-A nAb assay, is inferior compared with that in participants who received mRNA-1345 plus placebo at Day 1. The noninferiority in the GMT in participants who received mRNA-1345 coadministered with mRNA-1273.214 at Day 1 compared with that of participants who received mRNA-1345 plus placebo at Day 1 will be demonstrated by the LB of the 95% CI of the GMR of ruling out 0.667 (i.e., LB > 0.667) using noninferiority margin of 1.5. The GMR is the ratio of the GMT of RSV-A nAbs in participants who received mRNA-1345 coadministered with mRNA-1273.214 at Day 1 compared with the GMT of RSV-A nAbs in participants who received mRNA-1345 plus placebo at Day 1.

##### Co-primary endpoints based on Seroresponse Rate at Day 29:

The null hypothesis  $H_0^2$ : immunogenicity response to mRNA-1345 in participants who received mRNA-1345 coadministered with mRNA-1273.214 at Day 1, as measured by SRR of RSV-A nAbs at Day 29, is inferior compared with that in participants who received mRNA-1345 plus placebo at Day 1. The noninferiority in SRR in participants who received mRNA-1345 coadministered with mRNA-1273.214 at Day 1 compared with that of participants who received mRNA-1345 plus placebo at Day 1 will be demonstrated by the LB of the 95% CI of the SRR difference (coadministered group - mRNA-1345 plus placebo) of ruling out -10% (i.e., LB > -10%) using noninferiority margin of 10%.

Confidential

**Primary Objective to Evaluate the Impact on the Immune Response to SARS-CoV-2:**

Co-primary endpoints based on GMC at Day 29:

The null hypotheses  $H_0^3$  to  $H_0^4$ : immunogenicity response to mRNA-1273.214 in participants who received mRNA-1273.214 coadministered with mRNA-1345 at Day 1, as measured by GMC of nAbs for each of the 2 SARS-CoV-2 strains (Wuhan-Hu-1 and B.1.1.529) at Day 29, is inferior compared to that in participants who received mRNA-1273.214 plus placebo at Day 1. For each of the 2 SARS-CoV-2 strains, the noninferiority in the GMC in participants who received mRNA-1345 coadministered with mRNA-1273.214 at Day 1 compared with that of participants who received mRNA-1273.214 plus placebo at Day 1 will be demonstrated by the LB of the 95% CI of the GMR of ruling out 0.667 (i.e.,  $LB > 0.667$ ) using noninferiority margin of 1.5. The GMR is the ratio of the GMC of nAbs in participants who received mRNA-1345 coadministered with mRNA-1273.214 at Day 1 compared with the GMC of nAbs in participants who received mRNA-1273.214 plus placebo at Day 1.

Coprimary endpoints based on Seroresponse Rate at Day 29:

The null hypothesis  $H_0^5$  to  $H_0^6$ : immunogenicity response to mRNA-1273.214 in participants who received mRNA-1345 coadministered with mRNA-1273.214 at Day 1, as measured by SRR of nAbs for each of the 2 SARS-CoV-2 strains (Wuhan-Hu-1 and B.1.1.529) at Day 29, is inferior compared with that in participants who received mRNA-1273.214 plus placebo at Day 1. The noninferiority in the SRR in participants who received mRNA-1345 coadministered with mRNA-1273.214 at Day 1 compared with that of participants who received mRNA-1273.214 plus placebo at Day 1 will be demonstrated by the LB of the 95% CI of the SRR difference of ruling out 10% (i.e.,  $LB > -10\%$ ) using a noninferiority margin of 10%. The SRR difference in each strain is the SRR of SARS-CoV-2 nAb of the strain in participants who received mRNA-1345 coadministered with mRNA-1273.214 at Day 1 minus the SRR of SARS-CoV-2 nAb of the strain in participants who received mRNA-1273.214 plus placebo at Day 1.

**Key Secondary Objective to Evaluate the Impact on the Immune Response to RSV-B:**

Key secondary endpoint based on GMT at Day 29:

The null hypothesis  $H_0^7$ : immunogenicity response to mRNA-1345 in participants who received mRNA-1345 coadministered with mRNA-1273.214 at Day 1, as measured by GMT at Day 29 using RSV-B nAb assay, is inferior compared with that in participants who received mRNA-1345 plus placebo at Day 1. The noninferiority in the GMT in participants who received mRNA-1345 coadministered with mRNA-1273.214 at Day 1 compared with that of participants who received mRNA-1345 plus placebo at Day 1 will be demonstrated by the LB of the 95% CI of the GMR of ruling out 0.667 (i.e.,  $LB > 0.667$ ) using a noninferiority margin of 1.5. The GMR is the

Confidential

ratio of the GMT of RSV-B nAbs in participants who received mRNA-1345 coadministered with mRNA-1273.214 at Day 1 compared with the GMT of RSV- B nAbs in participants who received mRNA-1345 plus placebo at Day 1.

Hypothesis 7 will be assessed once all the primary hypotheses 1 to 6 are demonstrated.

**Key secondary endpoint based on SRR at Day 29:**

The null hypothesis  $H_0^8$ : immunogenicity response to mRNA-1345 in participants who received mRNA-1345 coadministered with mRNA-1273.214 at Day 1, as measured by SRR of RSV-B nAbs at Day 29, is inferior compared with that in participants who received mRNA-1345 plus placebo at Day 1. The noninferiority in the SRR in participants who received mRNA-1345 coadministered with mRNA-1273.214 at Day 1 compared with that of participants who received mRNA-1345 plus placebo at Day 1 will be demonstrated by the LB of the 95% CI of the SRR difference of ruling out -10% (i.e.,  $LB > -10\%$ ) using a noninferiority margin of 10%. The SRR difference is the SRR of RSV-B nAb in participants who received mRNA-1345 coadministered with mRNA-1273.214 at Day 1 minus the SRR of RSV-B nAb in participants who received mRNA-1345 plus placebo at Day 1.

Hypothesis 8 will be assessed once all the primary hypotheses and the primary and the key secondary hypothesis (i.e., hypotheses 1 to 7) are demonstrated.

The hierarchical order for the hypotheses to be tested is also indicated in [Figure 2](#)

**3.3.3. Sample Size and Power**

The study will plan to randomize approximately 1680 participants, with approximately 560 participants receiving mRNA-1345 plus placebo at Day 1 and receiving mRNA-1273.214 at Day 29 (Group 4), 560 participants receiving mRNA1345 plus mRNA-1273.214 at Day 1 and receiving placebo at Day 29 (Group 5), and 560 participants receiving mRNA-1273.214 plus placebo at Day 1 and receiving placebo at Day 29 (Group 6).

With approximately 560 participants in each group, the study has approximately 94% probability to observe at least 1 participant in the group with an AE at a true 0.5% AE rate.

**Sample Size and Power for the primary immunogenicity endpoints:**

Assuming approximately 10% of participants are ineligible to be included in the PP Set, there are 504 eligible participants in each group. The overall power considering meeting the primary objectives to evaluate the immune responses to RSV-A and influenza is 90%. Sample size justification for co-primary endpoints is shown in Table 4.

**Table 4: Sample Size Justification for the Co-primary Endpoints (Part B)**

Primary Endpoint	Number of Evaluable Participants (with 10% ineligible for Per-protocol Set)	$\alpha$	Standard Deviation	GMR/SRR Assumed	NI Margin	Power
mRNA-1345 Noninferiority (2-sided test)						
Day 29 GMT Coadministration (Group 5) vs mRNA-1345 alone at Day 1 (Group 4)	504 per group	0.05	1.5	GMR = 1	1.5	99%
Day 29 SRR Coadministration (Group 5) vs mRNA-1345 alone at Day 1 (Group 4)	504 per group	0.05		SRR = 0.8 in both groups	10%	97.8%
mRNA-1273.214 NI (2-sided test) for each SARS-CoV-2 strain (Wuhan-Hu-1 and B.1.1.529)						
Day 29 GMC Coadministration (Group 5) vs mRNA-1273.214 alone at Day 1 (Group 6)	504 per group	0.05	1.5	GMR = 1	1.5	99%
Day 29 SRR Coadministration (Group 5) vs mRNA-1273.214 at Day 1 (Group 6)	504 per group	0.05		SRR = 0.8 in both groups	10%	97.8%
Global power to show noninferiority of the coprimary immunogenicity endpoints						90%

- There is at least 99% power to demonstrate the noninferiority of the immune response to RSV-A, as measured by GMT of RSV-A nAb at Day 29 in participants receiving mRNA-1345 plus mRNA-1273.214 at Day 1 compared with that in participants receiving mRNA-1345 plus placebo at Day 1, at a 2-sided alpha of 0.05, assuming a noninferiority margin of 1.5 and an underlying GMR of 1. The SD of the natural log-transformed level is assumed to be 1.5.
- There is at least 97.8% power to demonstrate the noninferiority of the immune response, as measured by SRR of RSV-A nAbs at Day 29 in participants receiving mRNA-1345 plus mRNA-1273.214 at Day 1 compared with that in participants

receiving mRNA-1345 plus placebo at Day 1, at a 2-sided alpha of 0.05, assuming an SRR of RSV-A nAbs of 80% in both groups (a true SRR difference is 0), and a noninferiority margin of 10%.

- There is at least 99% power to demonstrate the noninferiority of the immune response to SARS-CoV-2, as measured by GMC of nAbs for each of the 2 SARS-CoV-2 strains (Wuhan-Hu-1 and B.1.1.529) at Day 29 in participants receiving mRNA-1345 plus mRNA-1273.214 at Day 1 compared with that in participants receiving mRNA-1345 plus placebo at Day 1, at a 2-sided alpha of 0.05, assuming a noninferiority margin of 1.5 and an underlying GMR of 1. The standard deviation of the natural log-transformed level is assumed to be 1.5.
- There is at least 97.8% power to demonstrate the noninferiority of the immune response to SARS-CoV-2, as measured by SRR of nAbs for each of the 2 SARS-CoV-2 strains (Wuhan-Hu-1 and B.1.1.529) at Day 29 in participants receiving mRNA-1345 plus mRNA-1273.214 at Day 1 compared with that in participants receiving mRNA-1273.214 plus placebo at Day 1, at a 2-sided alpha of 0.05, assuming an SRR of SARS-CoV-2 nAbs of 80% in both groups (a true SRR difference is 0), and a noninferiority margin of 10%.

#### **Sample Size and Power for the key secondary immunogenicity endpoints:**

Assuming approximately 10% of participants are ineligible to be included in the PP Set; 504 participants in each group for sample size in key secondary endpoints:

- There is at least 99% power to demonstrate the noninferiority of the immune response to RSV-B, as measured by GMT of RSV-B nAb at Day 29 in participants from Group 5 compared with that from Group 4, at a 2-sided alpha of 0.05, assuming a noninferiority margin of 1.5 and an underlying GMR of 1. The standard deviation of the natural log-transformed level is assumed to be 1.5.
- There is at least 97.8% power to demonstrate the noninferiority of the immune response, as measured by SRR of RSV-B nAbs at Day 29 in participants from Group 5 compared with that from Group 4, at a 2-sided alpha of 0.05, assuming a SRR of 80% in both groups (a true SRR difference is 0) and a noninferiority margin of 10%.

#### **3.3.4. Randomization**

The randomization will be in a blinded manner using a centralized IRT, in accordance with pre-generated randomization schedules. Randomization details is described in [Section 3.3.1](#).

### 3.3.5. Blinding and Unblinding

This is an observer-blind study. The investigator, study staff, study participants, site monitors, and Sponsor personnel (or its designees) will be blinded to the IP administered until the study database is locked and unblinded, with certain exceptions, please refer to Section 3.5.2 of the protocol and Data Blinding Plan for details.

Please see [Section 2.3.5](#) for details.

### 3.4. Analysis Populations

Please see [Section 2.4](#) for details, except of the following:

- Supportive PP Set will not be applicable in Part B.
- PP Set consists of all participants in the FAS who receive the assigned Day 1 study injections according to protocol regardless of Day 29 injection, comply with immunogenicity blood sampling to have a baseline and at least one Day 29 post-injection assessment within the visit window of study day [22, 43], and have no major protocol deviations that impact the immune response.
- Additionally, 2 subsets of the Solicited Safety Set are defined for Day 1 injection and Day 29 injection. Day 1 (Day 29) Solicited Safety Set consists of all participants in the Solicited Safety Set who have received the study injection on Day 1 (Day 29) and have contributed any solicited AR data (eDiary) from the time of study injection on Day 1 (Day 29) through the following 6 days.

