**Table 6: Analysis Sets**

Set	Description
Randomized Set	Includes all participants who are randomized in the study, regardless of the participant's treatment status in the study.

Set	Description
	Participants will be included in the vaccination group to which they are randomized.
Full Analysis Set (FAS)	All randomized participants who received any IP. Participants will be included in the vaccination group to which they are randomly assigned.
Per Protocol (PP) Set	Includes all participants in the FAS that received the assigned IP dose according to protocol, complied with immunogenicity blood sampling to have a baseline and at least 1 post-injection assessment, and have no major protocol deviations that impact the immune response. The PP Set will be the primary population used for the analysis of immunogenicity data. Participants will be included in the vaccination group to which they are randomly assigned.
Solicited Safety Set	Includes all randomized participants who received any study vaccination and contributed any solicited AR data. The Solicited Safety Set will be used for the analyses of solicited ARs and participants will be included in the vaccination group corresponding to the IP they actually received.
Safety Set	Includes all randomized participants who receive any study injection. Participants will be included in the vaccination group corresponding to the IP they actually received for the analysis of safety data using the Safety Set.

Abbreviations: AR = adverse reaction; FAS = full analysis set; IP = investigational product; PP = per protocol.

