### **2.4.3. Per-protocol Set**

#### **PP Set**

The PP Set consists of all participants in the FAS who receive the assigned study injections according to protocol, comply with immunogenicity blood sampling to have a baseline and at least one Day 29 post-injection assessment within the visit window of study day [22, 43], and have no major protocol deviations that impact the immune response.

The PP Set will be the primary population used for the analysis of immunogenicity data, and Participants will be included in the vaccination group to which they are randomly assigned.

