#### **Vaccination groups:**

The following vaccination groups will be used for summary purposes:

- D1: mRNA-1345 (█ CC1 µg) + placebo and D29: mRNA-1273.214 (█ CC1 µg)
- D1: mRNA-1345 (█ CC1 µg) + mRNA-1273.214 (█ CC1 µg) and D29: placebo
- D1: mRNA-1273.214 (█ CC1 µg) + placebo and D29: placebo

If a subject receives any dose of mRNA-1345 on Day 1, regardless of the vaccination group the subject is randomized to, the subject will be included in the actual vaccination group received (mRNA-1345 (█ CC1 µg) + placebo/ mRNA-1273.214 (█ CC1 µg) or mRNA-1345 (█ CC1 µg) + mRNA-1273.214 (█ CC1 µg)/ placebo) for safety and reactogenicity analyses. Similar logic will be applied for a subject who receives any dose of mRNA-1273.214.

All analyses and data summaries/displays for disposition, demographics and baseline characteristics, safety and immunogenicity will be provided by vaccination group using appropriate analysis population, unless otherwise specified. Local solicited adverse reactions after Day 1 injection will be also summarized by injection content (mRNA-1345, Placebo and mRNA-1273.214).

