## **3.5.4. Immunogenicity Analysis**

The analyses of immunogenicity will be using the PP Set, by vaccination group. The supportive analyses of immunogenicity especially for primary immune response may be conducted using the FAS based on [Appendix I](#). If the number of participants in the FAS and PP Set differ (defined as the difference divided by the total number of participants in the PP Set) by more than Confidential

10%, additional supportive analyses of non-primary immunogenicity may be conducted using the FAS.

Please see [Section 2.5.4](#) for calculations of GMT, GMC, and GMFR.

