#### **3.5.4.4. Analysis of Other Secondary Immunogenicity Endpoints**

The secondary immunogenicity endpoints include the following:

- GMT and GMFR of post-injection/baseline titers to RSV-A nAbs up to Day 211/EoS
- GMT and GMFR of post-injection/baseline titers to RSV-B nAbs up to Day 211/EoS
- SRR and proportion of participants with  $\geq$  2-fold increases in RSV-A nAb titers up to Day 211/EoS
- SRR and proportion of participants with  $\geq$  2-fold increases in RSV-B nAb titers up to Day 211/EoS
- GMC and GMFR of post-injection/baseline concentration to SARS-CoV-2 nAbs up to Day 211/EoS
- SRR and proportion of participants with  $\geq$  2-fold increases in SARS-CoV-2 nAb up to Day 211/EoS

The statistical analyses are:

- GMT of RSV-A nAbs and RSV-B nAbs and GMC of SARS-CoV-2 nAbs for each SARS-CoV-2 strain (Wuhan-Hu-1 and B.1.1.529) with corresponding 95% CI will be provided at Baseline (Day 1), Day 29, Day 57, Day 181, and Day 211/EoS by vaccination group. The 95% CIs will be calculated based on the t-distribution of the log-transformed values and then back transformed to the original scale for presentation. The following descriptive statistics will also be provided at Baseline (Day 1), Day 29, Day 57, Day 181, and Day 211/EoS: the number of participants (n), median, minimum and maximum. GMT or GMC with 95% CI will be plotted at Baseline (Day 1) and Day 29 by vaccination group. Reverse cumulative distribution function plot may also be provided.
- GMFR of RSV-A nAbs, RSV-B nAbs, and SARS-CoV-2 nAbs for each SARS-CoV-2 strain (Wuhan-Hu-1 and B.1.1.529) with corresponding 95% CI will be provided at Day 29, Day 57, Day 181, and Day 211/EoS over pre-injection at Day 1 [baseline] by vaccination group. The 95% CIs will be calculated based on the t-distribution of the difference in the log-transformed values (post-baseline time point – Day 1) and then back

transformed to the original scale for presentation. GMFR with 95% CI will be plotted at Day 29 by vaccination group.

- Proportion of participants with  $\geq$  2-fold increases from Day 1 (baseline) in RSV-A nAb titers, RSV-B nAb titers, and SARS-CoV-2 nAbs for each SARS-CoV-2 strain (Wuhan-Hu-1 and B.1.1.529) at Day 29, Day 57, Day 181, and Day 211/EoS will be provided with 2-sided 95% CIs using the Clopper-Pearson method by vaccination group.

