- SRR in RSV-A nAb titers, RSV-B nAb titers, and SARS-CoV-2 nAbs for each SARS-CoV-2 strain (Wuhan-Hu-1 and B.1.1.529) at Day 29, Day 57, Day 181, and Day 211/EoS will be provided with 2-sided 95% CIs using the Clopper-Pearson method by vaccination group.

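### Part B's per-protocol set does not require the Day 29 injection, so Group 4's SARS-CoV-2 summaries after Day 29 can count people who never received mRNA-1273.214

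*SAP*

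**What the plan says.** - **Who is in the set.** Protocol Table 6, which covers Parts A and B, defines the PP Set with the condition "Includes all participants in the FAS that received the assigned IP dose according to protocol" and makes no exception for a second injection day. SAP 3.4 replaces this for Part B with those who "receive the assigned Day 1 study injections according to protocol regardless of Day 29 injection". They must also have a baseline sample, a Day 29 sample in the window, and no major deviation that affects the immune response.
- **Where it is used.** SAP 3.5.4: "The analyses of immunogenicity will be using the PP Set, by vaccination group". No other per-protocol set is defined for later visits.
- **Which group they count in.** SAP 2.4.3, carried into Part B by SAP 3.4: "Participants will be included in the vaccination group to which they are randomly assigned".
- **What is reported late.** Under SAP 3.5.4.4, GMTs and the SARS-CoV-2 GMC "will be provided at Baseline (Day 1), Day 29, Day 57, Day 181, and Day 211/EoS by vaccination group". Seroresponse rates "at Day 29, Day 57, Day 181, and Day 211/EoS will be provided with 2-sided 95% CIs using the Clopper-Pearson method by vaccination group". GMFR and the 2-fold rise use the same post-baseline visits. The exploratory binding-antibody analyses (SAP 3.5.4.5) follow the same methods.
- **How Group 4 is labelled.** SAP 3.5.1 describes it as mRNA-1345 plus "placebo and D29: mRNA-1273.214". SAP Table 3 shows that this is the group's only mRNA-1273.214 dose.

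**The concern.** A set built for Day 29 endpoints is reused for visits at which the Day 29 injection is the exposure being described. Up to the Day 29 sample, whether that injection follows is irrelevant. From Day 57 on, it is the whole reason for Group 4 to show a response to mRNA-1273.214.

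The case is foreseen in the plan. Protocol 2.6.1.1, applied to Part B by 3.6.1.1, allows an injection to be withheld. Protocol 2.5.4 has the reason for a missed dose recorded. SAP 3.5.2.1 counts Day 1 and Day 29 injections separately, and SAP 3.5.3.2.2 tabulates adverse events leading to discontinuation of study vaccine. A participant who gives the Day 29 sample, is not injected, and attends later visits stays in the PP Set under Group 4's label.

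At stake is the accuracy of one set of per-protocol summaries. Group 4 is the only arm given mRNA-1273.214 four weeks after mRNA-1345, and Day 57 is its first scheduled SARS-CoV-2 sample after that dose.

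**Working it through.** **1. The plan's own figures, and whether they are touched.** Inputs from SAP 3.3.3 and Table 4: 560 per group, 10% excluded, SD 1.5 on the natural-log scale, margin 1.5, GMR 1, SRR 80% in both groups with a 10-point margin, two-sided alpha 0.05.

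- Evaluable n = 560 × 0.9 = 504 per group.
- GMT/GMC: SE = 1.5 × √(2/504) = 0.0945; power = Φ(ln 1.5 / 0.0945 − 1.96) = 99.0% (stated 99%).
- SRR: SE = √(2 × 0.8 × 0.2 / 504) = 0.0252; power = Φ(0.10 / 0.0252 − 1.96) = 97.8% (stated 97.8%).
- All six co-primary endpoints, taken as independent: 0.990³ × 0.978³ = 90.7% (stated 90%).

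These all concern Day 29 samples. Footnote e of Protocol Table 7 requires blood to be drawn before the injection on vaccination days, so neither the problem nor the fix changes them.

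**2. Size of the distortion after Day 29.** Let q be the share of Group 4 PP participants with a late sample but no Day 29 injection. Let f be the ratio of geometric mean concentrations, recipients to non-recipients, at that visit. Neither value is in the documents; both are assumptions. On the log scale the group mean falls by q × ln f, so the GMC is multiplied by f^(−q). The GMFR changes by the same factor if Day 1 baselines are alike.

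| q | about n of 504 | f = 2 | f = 4 | f = 8 |
|---|---|---|---|---|
| 1% | 5 | 0.993 | 0.986 | 0.979 |
| 5% | 25 | 0.966 | 0.933 | 0.901 |
| 10% | 50 | 0.933 | 0.871 | 0.812 |

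For q from 1% to 5% and f from 4 to 8, the GMC is 1.4% to 9.9% too low. The 2-fold column and the 10% row show how far this moves under other assumptions.

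**3. Seroresponse.** Take 80% among recipients, which is the SAP's Day 29 planning value for Groups 5 and 6, borrowed here. If a share r responds without the dose, the loss is q × (0.80 − r). The upper limit is at r = 0: the rate is 0.80 × 0.99 = 79.2% at q = 1% and 0.80 × 0.95 = 76.0% at q = 5%, a loss of 0.8 to 4.0 points. Any response without the dose makes it smaller. This calculation fits Day 57 best.

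**4. Does another clause remove these participants?**

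- The major-deviation clause in SAP 3.4 may remove some, but a withholding that the protocol permits need not be a deviation.
- The intercurrent events in SAP Table 8 all occur before Day 29; a missed Day 29 injection is not among them.
- Disposition tables show how many received the injection, but do not change the PP denominator.
- SAP 3.4 does make this adjustment for reactogenicity: its Day 29 Solicited Safety Set requires the Day 29 injection. Immunogenicity has no counterpart.

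**The case against.** The strongest reply is that nothing confirmatory rests on these numbers. Every SARS-CoV-2 hypothesis (SAP 3.3.2) and estimand (7a to 8b, SAP Table 11) compares Group 5 with Group 6, both given mRNA-1273.214 on Day 1. Group 4's later dose is there so that all participants receive the booster. At Day 57 Group 4 is 57 − 29 = 28 days past its dose and Groups 5 and 6 are 57 − 1 = 56 days past theirs, so no planned contrast sets them side by side. SAP 3.5.5 leaves these endpoints outside multiplicity control. All of this stands, and it limits the point to descriptive results.

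The possible shift is also modest against sampling error. With SD 1.5 and n = 504, the 95% interval for one group's GMC is exp(±1.96 × 1.5/√504), about −12% to +14%. The SRR half-width is 1.96 × √(0.8 × 0.2/504), about 3.5 points. This also stands, but the shift is systematic and the interval does not reveal it.

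Two stronger readings go beyond the text. A reader might call the affected people unvaccinated. Part B inclusion criterion 2 requires a complete COVID-19 primary series, so they lack the study booster only. A reader might also infer that Group 5 or 6 participants given mRNA-1273.214 by mistake on Day 29 stay in the set. That is not established: dose deviations are tracked (Protocol 2.7.7), and the sponsor excludes those with major deviations before database lock and unblinding (SAP 2.5.2.7).

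Finally, SAP Section 1 says that the SAP prevails over the protocol. That settles which definition applies. It does not replace the listing that Protocol 3.8 calls for in the SAP or CSR when secondary analyses change; none of the four changes in SAP Section 5 is this one.

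**Conclusion.** The point holds for Group 4's SARS-CoV-2 summaries at Days 57, 181 and 211, and only there. As written, the rule lets participants who did not receive the Day 29 booster be summarised as recipients, and this pulls the group's per-protocol GMC, GMFR, 2-fold rise and seroresponse downward. Under the assumed 1% to 5% missed and 4- to 8-fold rise, the GMC is about 1% to 10% low. Seroresponse is at most 0.8 to 4 points low, if the rate is 80% among recipients and no one responds without the dose. The true size is unknown until the Day 29 dosing data are tabulated within the PP Set.

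A reader might infer that the Part B noninferiority conclusions or their power are compromised. The documents do not support that: those tests use Day 29 samples taken before the injection. Nor is a comparison between groups biased, since no planned SARS-CoV-2 comparison includes Group 4. The change is worth making because a per-protocol label should describe the regimen received, and the correction is cheap.

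**What to change.** - **SAP 3.4 and 3.5.4.4.** Keep the present PP Set for all Day 29 endpoints, all RSV summaries, and all Group 5 and 6 summaries. For Group 4's SARS-CoV-2 neutralizing antibody summaries at Days 57, 181 and 211, include only PP participants who received the assigned Day 29 mRNA-1273.214 injection. Apply the same restriction to the binding-antibody summaries in SAP 3.5.4.5, if they are produced.
- **Do not extend the condition to Groups 5 and 6.** It would drop participants who missed only a placebo from the persistence data of the two groups whose comparison matters.
- **SAP Section 5.** List the departure from Protocol Table 6: the Day 29 injection is not required for the Part B PP Set, except in the Group 4 summaries named above.

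The cost is a sentence or two, a flag from dosing data already collected, and a slightly smaller Group 4 at late visits. The Group 4 population will then differ between Day 29 and later visits, and the restriction selects on an event after randomization. A table footnote giving the number excluded would make both visible. Hypotheses, alpha, sample size and power do not change.
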